13.3.2 Operating Characteristics

Information in this section is based on a simulation study, the results of which are on file at PPD.

When 3 mcg and all higher doses are unsafe, the model described above has an average sample of 9.2 patients.

When all doses are safe, the model will recommend stopping after an average of 24.5 patients (80th centile 33 patients).

The simulation study also investigated a range of dose-toxicity scenarios with the true MTD located at the low end of the dose range, at the high end of the dose range and in the middle of the dose range. Relatively steep and relatively gentle slopes were considered. The average sample size was only slightly affected by the gradient of the dose-toxicity curve and ranged from 26.9 (80th centile 27) when the true MTD was at the lower end of the dose-toxicity curve to 27.8 (80th centile 33) when the true MTD was at the upper end.

The chance that the model identified as the MTD a dose which truly was in the target toxicity band ranged from 64% to 42% depending on whether the true MTD was at the lower or upper end of the dose range.

13.3.3 Sample Paths

The tables in this section ([Table 13-9](#), [Table 13-10](#), [Table 13-11](#), and [Table 13-12](#)) illustrate various possible paths of dose recommendation and state of the N-CRM model given various response patterns that might be observed in the study.

Table 13-9: Scenario 1, No DLT Reported at Any Dose

Dose (mcg)	Number of DLTs / Number of Patients Treated	Estimated MTD	Recommended Next Dose
3	0 / 3	38	10
10	0 / 3	67	30
30	0 / 3	185	100
100	0 / 3	198	195
195	0 / 3	>200	200

DLT = dose-limiting toxicity; MTD = maximum tolerated dose.

Table 13-10: Scenario 2, One DLT Reported at 30 mcg Dose

Dose (mcg)	Number of DLTs / Number of Patients Treated	Estimated MTD	Recommended Next Dose
3	0 / 3	38	10
10	0 / 3	67	30
30	1 / 3	185	100
25	0 / 3	35	35
35	0 / 3	77	75
75	0 / 3	148	145
145	0 / 3	>200	200
200	0 / 3	>200	200
200	0 / 3	>200	Stop

DLT = dose-limiting toxicity; MTD = maximum tolerated dose.

Table 13-11: Scenario 3, Two DLTs Reported at 100 mcg Dose

Dose	Number of DLTs / Number of Patients Treated	Estimated MTD	Recommended Next Dose
3	0 / 3	38	10
10	0 / 3	67	30
30	0 / 3	185	100
100	2 / 3	61	60
60	0 / 3	70	70
70	0 / 3	78	75
75	0 / 3	87	85
85	0 / 3	100	100
100	2 / 3	83	80
80	0 / 3	87	85
85	0 / 3	91	90
90	0 / 3	97	Stop

DLT = dose-limiting toxicity; MTD = maximum tolerated dose.

Table 13-12: Scenario 4, One DLT at 30 mcg, 2 DLTs at 145 mcg and 2 DLTs at 100 mcg Dose

Dose	Number of DLTs / Number of Patients Treated	Estimated MTD	Recommended Next Dose
3	0 / 3	38	10
10	0 / 3	67	30
30	0 / 3	28	25
25	1 / 3	35	35
35	0 / 3	77	75
75	0 / 3	148	145
145	2 / 3	87	85
85	0 / 3	99	95
95	0 / 3	109	105
105	2 / 3	93	90
90	0 / 3	99	Stop

DLT = dose-limiting toxicity; MTD = maximum tolerated dose.

13.4 Schedule of Cycle 1 Assessments, Intra-Patient Escalation Regimen

Patients who receive IPE should follow the schedule below during Cycle 1, and the main schedule at all other times, including Pre-Screening, Screening, Cycle 2 and subsequent treatment cycles, and Follow-up.

The Cycle 1 schedule is provided in [Table 13-13](#). Assessments marked “X” should be performed prior to dosing. Assessments that are to be performed at multiple timepoints are marked with the number of timepoints (including optional timepoints, if applicable) for the visit (eg, 2× is twice) and details of the timepoints are provided in the footnote. Additional details regarding the assessments are provided in [Section 7.4](#).

Table 13-13: Schedule of Cycle 1 Assessments, IPE Regimen

Procedure	Cycle 1						
Day of Cycle	1	2	8	9	15	16	22
Adverse events	X	X	X	X	X	X	X
Concomitant medications	X	X	X	X	X	X	X
Safety Assessments							
Complete physical examination	X						
Abbreviated physical examination			X		X		X
Weight	X						
Vital signs		~14×		~14×		~14×	3×
12-lead ECG (single)	2×						
ECOG performance status	X						
Hematology panel	X	X	X	X	X		X
Chemistry panel	X		X		X		X
Thyroid function	X						
Urine pregnancy test (women of childbearing potential)	X						
PK and Immunogenicity Assessments							
Pharmacokinetic sampling	3×	X	8×	X	8×	X	3×
Immunogenicity sampling	X		X		X		
[REDACTED]		Between C1D9 and C1D16 (required for ≥ 10 patients in Phase II, optional for all other patients)					
[REDACTED]							

Procedure	Cycle 1					
IMCnyeso Administration						
One-step IPE	C1D1 dose level		Target dose level		Target dose level	Target dose level
Two-step IPE	C1D1 dose level		C1D8 level		Target dose level	Target dose level

AE = adverse event; C#D# = Cycle # Day #; CRS = cytokine release syndrome; [REDACTED]; ECG = electrocardiogram; ECOG = Eastern Cooperative Oncology Group; EOI = end of infusion; hr = hour(s); min = minutes; [REDACTED] PK = pharmacokinetics; [REDACTED]

ECG assessments are to be done pre-dose and within 1 hour of EOI on indicated days.

Vitals (body temperature, pulse, respiratory rate, blood pressure; oxygen saturation should also be assessed for \geq first 3 cycles of treatment), are to be assessed at the following timepoints:

- C1D1/C1D2, C1D8/C1D9, and C1D15/C1D16: pre-dose (within 2 hours), EOI (within 15 min), every 2 hours (\pm 15 min) through 8-hour post-EOI, then every 4 hours (\pm 30 min) until discharge
- C1D22: pre-dose (within 2 hours), EOI (within 15 min), and 1-hour post-EOI (\pm 15 min)

Pharmacokinetics samples are to be collected at the following timepoints:

- C1D1: pre-dose (within 2 hours), EOI (within 15 min), 8-hour post-EOI (\pm 1 hr)
- C1D8 and C1D15: pre-dose (within 2 hours), EOI (within 15 min), 1-hour post-EOI (\pm 15 min), 2-hour post-EOI (\pm 15 min), 4-hour post-EOI (\pm 15 min), 6-hour post-EOI (\pm 30 min), 8-hour post-EOI (\pm 1 hr), and 12-hour post-EOI (optional, \pm 3 hr)
- C1D2, C1D9, and C1D16: 24-hour post-EOI (\pm 4 hr)
- C1D22: pre-dose (within 2 hours), EOI (within 15 min), 8-hour post dose (\pm 1 hr)

Central lab cytokine testing samples are to be collected at the following timepoints:

- C1D1: pre-dose (within 2 hours) and 4-hour post-EOI (\pm 15 min)
- C1D8 and C1D15: pre-dose (within 2 hours), 4-hour post-EOI (\pm 15 min), 8-hour post-EOI (\pm 1 hr), and 12-hour post-EOI (optional, \pm 3 hr)
- C1D2, C1D9, and C1D16: 24-hour post-EOI (\pm 4 hr)
- C1D22: pre-dose (within 2 hours) and 4-hour post-EOI (\pm 15 min)
- Additional samples may be collected if a patient has suspected CRS. Recommended timepoints are within 5 hours and 1 week after onset of CRS.

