Rash/Pruritus and Skin Toxicity: Effects in human melanocytes were noted in the non-clinical toxicology studies at IMCnyeso concentrations of 500 pM (100-fold above MABEL). In this FIH study, special attention is placed on the monitoring of adverse effects of IMCnyeso in the skin and conservative management guidance and DLT criteria are implemented for the effects of IMCnyeso in the skin.

Local tumor inflammation: Based on the mechanism of action of IMCnyeso, it may cause inflammation within the tumor microenvironment. Depending on the location of the tumors, various AE may occur, including:

- **Hepatic Events:** Increased transaminase levels may be observed, especially in patients with liver metastasis. Increased bilirubin may also be observed.
- **Pulmonary Events:** Patients with lung metastasis may experience events such as dyspnea, pulmonary edema, pulmonary infiltrates, or pleural effusion.
- **Tumor Flare/Pain:** Severe pain at the site of known tumors is predicted with IMCnyeso, especially following the first 1-4 weekly (QW) doses. Patients receiving tebentafusp have required admission for IV pain medication.

Lymphopenia: Monitoring of patients' white cell counts will be conducted during the study of IMCnyeso. It is important to note that the trafficking of lymphocytes is a desired effect of IMCnyeso. The lymphopenia observed with tebentafusp has been shown to be transient and self-resolving, with lymphocyte counts returning to baseline levels by Day 8.

Full details can be found in the single reference safety document, which is the current IMCnyeso Investigator's Brochure.

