4 STUDY OBJECTIVES AND ENDPOINTS

Study objectives and corresponding endpoints are shown in [Table 4-1](#).

Table 4-1: Study Objectives and Endpoints

Objectives	Endpoints
Primary - Phase I	
To identify the MTD and/or the RP2D of IMCnyeso, as a monotherapy, when administered weekly to patients with advanced NSCLC, melanoma, urothelial cancer, and synovial sarcoma	Incidence of dose-limiting toxicities Incidence and severity of AE and SAE Changes in laboratory parameters, vital signs, and ECGs Dose interruptions, reductions, and discontinuations
Primary – Phase II	
To assess the preliminary anti-tumor activity of IMCnyeso as monotherapy in advanced NSCLC, urothelial cancer, and synovial sarcoma	BOR as determined by RECIST v1.1
Secondary- Phase II	
To characterize the safety and tolerability of IMCnyeso	Incidence and severity of AE and SAE Changes in laboratory parameters, vital signs, and ECGs Dose interruptions, reductions, and discontinuations
Secondary- Phase I and Phase II	
To assess the preliminary anti-tumor activity of IMCnyeso as monotherapy	Phase I: BOR, PFS, and DoR by RECIST v1.1; OS Phase II: PFS, and DoR by RECIST v1.1; OS
To characterize the PK profile of IMCnyeso as monotherapy	Serum PK parameters (eg, AUC, C _{max} , T _{max} , t _{1/2}) after single and multiple doses
To evaluate the preliminary incidence of anti-IMCnyeso antibody formation following multiple infusions of IMCnyeso	Incidence of anti- IMCnyeso antibody formation and its impact on PK
Exploratory	
[REDACTED]	[REDACTED]

Objectives	Endpoints
[REDACTED]	[REDACTED] [REDACTED] [REDACTED]
[REDACTED]	[REDACTED] [REDACTED] [REDACTED]

AE = adverse event; AUC = area under the curve; BOR = best overall response; CD# = cluster of differentiation #; C_{max} = maximum observed concentration; [REDACTED]; [REDACTED]; DoR = duration of response; ECG = electrocardiogram; [REDACTED]; [REDACTED]; MTD = maximum tolerated dose; NSCLC = non-small cell lung cancer; [REDACTED]; PFS = progression-free survival; PK = pharmacokinetic; RECIST = Response Evaluation Criteria in Solid Tumors; [REDACTED]; RP2D = recommended Phase II dose; SAE = serious adverse event; t_{1/2} = terminal elimination half-life; [REDACTED]; T_{max} = time of maximum concentration; [REDACTED].

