6.10.1 Intra-Patient Escalation

A recent FDA review concluded that incorporation of a step dose / IPE can result in better patient tolerance of higher doses of CD3 bispecific molecules ([Saber, 2017](#)) due to a phenomenon of induced tolerance or tachyphylaxis. IPE regimens are used for the related ImmTAC molecule tebentafusp as well as the approved CD3 bispecific blinatumomab.

If the severity of cytokine-mediated AEs tend to become less severe following the initial doses of study drug using a fixed-dose regimen, the SST may initiate a 1-step IPE regimen, in which a lower dose is given on Cycle 1 Day 1 and a higher (target) dose is given on Cycle 1 Day 8 and beyond, as shown in [Figure 6-1](#).

[figure not shown]

Figure 6-1: Schematic Illustration of a 1-Step IPE Regimen

Rules for the 1-step IPE regimen are as follows:

- The initial target dose level must be a permitted escalation step based on BLRM output and the consensus of the SST
- The initial target dose level must not exceed the fixed-dose MTD (if established)
- The C1D1 dose level must be at least one dose level below the initial target dose, and must be a dose level that has been evaluated in ≥ 3 patients using a fixed-dose regimen, with a decision to escalate based on the BLRM output and SST review of all available relevant data.
- Escalation of the target dose in subsequent cohorts may proceed as in the main dose escalation:
 - Separate MTD/RP2D may be identified using fixed-dose and 1-step IPE regimens
 - DLT will be attributed to the dose level of the most recently administered dose prior to onset of the DLT (eg, a DLT with onset on C1D4 would be attributed to the C1D1 dose level, while a DLT with onset on C1D10 would be associated to the C1D8 dose level)
- The dose level for C1D1 remains fixed for all subsequent cohorts
- Patients receiving IPE must receive the C1D1 dose prior to receiving the target dose
- If a 1-step IPE regimen is evaluated in Phase I, it may be selected for further evaluation in Phase II

Experience with other CD3 bispecific molecules (including tebentafusp and blinatumomab) indicates that multi-step IPE may mitigate the risk of a cytokine-mediated AE more effectively than a 1-step IPE or fixed-dose regimen. If further mitigation of cytokine-mediated events is desired, the SST may decide to evaluate a two-step IPE regimen, in which an intermediate dose is given on Cycle 1 Day 8, as shown in [Figure 6-2](#).

[figure not shown]

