10.3 Pharmacodynamics

Cytokines and lymphocytes are analyzed and are covered by this SAP. No other pharmacodynamics analysis would be performed.

11 Interim Analysis

No formal interim analysis is planned during Phase I. The BLRM will be updated after each dose-escalation cohort and the MTD / RP2D will be determined at the end of Phase I (see Section 3.1).

A formal interim analysis will be conducted during Phase II. ORR will be evaluated for the first 9 patients in each Phase II cohort to determine whether enrollment may continue (see Section 4.1).

12 Changes in the Planned Analysis

There were no substantial changes from the planned analyses described in the protocol version 4.0, dated 24 Feb 2020 to those presented in this SAP. The following minor detail has changed from the protocol:

- All Patients Set has been added to allow for additional disposition summaries to be conducted
- Safety RP2D Analysis Set has been added to allow for some analyses to be conducted on patients pooled across phases if they receive RP2D.

13 References

14 Appendices

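### Under intra-patient escalation, no post-infusion ECG at the target dose is scheduled within the 28-day DLT window, and under 2-step escalation no hematology panel follows the first target dose for 7 days

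*Protocol*

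**What the plan says.** Table 4-1 of the protocol lists "Changes in laboratory parameters, vital signs, and ECGs" among the Phase I primary endpoints that support the choice of MTD and RP2D.

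Section 13.4 replaces the Cycle 1 schedule, "Patients who receive IPE should follow the schedule below during Cycle 1", and returns to the main schedule (Table 7-2) from Cycle 2. In Table 13-13 the ECG row reads "12-lead ECG (single) 2" times, marked under Day 1 only. The footnote adds: "ECG assessments are to be done pre-dose and within 1 hour of EOI on indicated days". The hematology row, "Hematology panel X X X X X X", has six marks across seven day columns (1, 2, 8, 9, 15, 16, 22), and the empty cell is Day 16. A mark on a dosing day means a pre-dose sample.

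Section 6.10.1 sets the dosing order. For 1-step IPE, "The C1D1 dose level must be at least one dose level below the initial target dose", and the target is given from C1D8. For 2-step IPE an intermediate dose is given on C1D8 and the target from C1D15. A DLT is attributed to the latest dose given before onset. Section 6.10.2 fixes a 28-day DLT window for every regimen and requires at least two target-level doses for a DLT-free patient to count.

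On lymphocytes, Section 1.4 describes the fall seen with the related molecule as transient, "with lymphocyte counts returning to baseline levels by Day 8". SAP Section 10.3 states: "Cytokines and lymphocytes are analyzed and are covered by this SAP".

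**The concern.** In the fixed-dose schedule, Day 1 is the first dose at the level being judged, so a Day 1 ECG pair and a Day 2 hematology panel are well placed. Table 13-13 moves other intensive monitoring to follow the target dose. The eight-point PK profile is on C1D8 and C1D15, frequent vital signs run through C1D15/C1D16, and 24-hour PK and cytokine samples are taken on Day 16. ECG and hematology keep the fixed-dose days, and no reason is given.

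As a result, the post-infusion cardiac data that the schedule yields inside the DLT window describe the lead-in dose. SAP Section 8.5 summarizes QTcF as a shift from baseline to the worst on-treatment value. For a patient who stops during Cycle 1, that worst value rests on the lead-in ECG and an end-of-treatment ECG, and the end-of-treatment visit may fall up to 14 days after the last dose. An IPE regimen may also be taken into Phase II, where the same table would apply.

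**Working it through.** The plan states no figure on this point, so the check is a calendar count.

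**Inputs**
- ECG days in Cycle 1: Day 1 only (Tables 7-2 and 13-13).
- Hematology days in Cycle 1: 1, 2, 8, 9, 15, 22 (both tables).
- Dose days: 1, 8, 15, 22, with at least 7 days between doses (Section 7.2).
- Target-dose days: fixed 1, 8, 15, 22; 1-step 8, 15, 22; 2-step 15, 22.
- DLT window: Days 1 to 28 (Section 6.10.2).

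**Next ECG.** The earliest C2D1 is 1 + 4 × 7 = Day 29.

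| Regimen | Post-infusion ECGs on a target-dose day, Days 1–28 | Target doses before C2D1 | First hematology after first target dose |
|---|---|---|---|
| Fixed | 1 (Day 1) | 4 | Day 2 (2 − 1 = 1 day later) |
| 1-step | 0 | 3 | Day 9 (9 − 8 = 1 day later) |
| 2-step | 0 | 2 | Day 22, pre-dose (22 − 15 = 7 days later) |

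**Day 28 exception.** Section 7.2 lets safety assessments be done up to 24 hours before dosing, so the C2D1 pre-dose ECG could be taken on Day 28. That is 28 − 22 = 6 days after the last dose. The amendment rationale gives a half-life under 24 hours for this drug class. Taking 24 hours as the upper bound, at most 0.5^6 = 0.016 of the peak, about 1.6%, would remain. It is a trough reading.

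**Lymphocytes.** Recovery by Day 8 is 8 − 1 = 7 days after a Day 1 dose. The 2-step Day 22 sample is also 7 days after the first target dose, when recovery would be expected.

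**Patients (SAP Table 1)**
- Phase I total: 4 + 3 + 5 + 3 + 5 + 4 + 6 = 30.
- IPE cohorts 5 to 7: 5 + 4 + 6 = 15, of whom 9 are enrolled and 6 planned.
- 2-step at 180 and 300 mcg: 4 + 6 = 10, of whom 4 are enrolled and 6 planned.
- Cohort 5 (n = 5) has a 100 mcg target, a level given as a first dose with ECGs in fixed-dose cohort 4 (n = 3).
- In cohorts 6 and 7 the Day 1 dose is 30 mcg, so the in-window post-infusion ECG is at 30/180 = one sixth or 30/300 = one tenth of target.

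**The case against.** The strongest reply is that nothing is decided on Cycle 1 ECGs alone. Patients who stay on treatment have ECG pairs at C2D1 and on Day 1 of each cycle through Cycle 6. The Study Safety Team meets after the whole cohort has completed DLT evaluation and reviews all available data. The first two patients at a level start at least a week apart, and the RP2D needs at least six patients, so some C2D1 ECGs should be in hand. This largely stands. It is weakest for the last patients enrolled, because the SAP's Phase I summary report may be cut once everyone has completed DLT evaluation, and for those who stop early.

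A C2D1 ECG within an hour of infusion is also near peak concentration at the target dose. The protocol describes tolerance for cytokine-mediated events, not ECG intervals, and names no expected cardiac signal. That stands too: C2D1 is a valid reading at the dose, but a late one.

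Overnight stays, frequent vital signs, telemetry for Grade 2 or higher CRS, and unscheduled tests give clinical cover. The telemetry and unscheduled tests are event-driven and do not supply systematic data for a primary endpoint. The redacted rows in Table 13-13 do not explain the gap, since the ECG and hematology rows are legible.

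Three stronger readings are tempting and are not supported:
- A reader might infer that no ECG at all can fall inside the window after a target dose. A pre-dose trough ECG can, on Day 28.
- A reader might infer that the MTD model is compromised. It uses DLTs, and Table 6-3 has no ECG-specific row; an ECG event would enter only through the general Grade 3 rule.
- A reader might infer that the hematology gap hides DLTs. Lymphopenia counts only at Grade 3 or higher with infection, and Day 22 is inside the window.

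**Conclusion.** The gap is real and should be closed. For all 15 IPE patients, no scheduled post-infusion ECG at the target dose falls within 28 days, against one under fixed dosing. The practical weight lies with the 10 patients at 180 and 300 mcg, because 100 mcg already has fixed-dose ECGs. The hematology gap is separate and confined to those same 10 patients on 2-step IPE. It weakens laboratory and lymphocyte data more than DLT calls.

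This rests on Table 13-13 as printed, on scheduled assessments only, and on the related molecule's lymphocyte time course applying here. It does not show that cardiac risk is present, or that the target doses go without ECGs in patients who reach Cycle 2.

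**What to change.** In Table 13-13:
- Keep the C1D1 pre-dose ECG. Protocol Section 9.1 and SAP Section 4 define baseline as the last assessment before the first dose. Moving the whole pair would leave IPE patients with a Screening baseline up to 21 days old, unlike the fixed-dose cohorts.
- Move the post-infusion ECG (within 1 hour of end of infusion) from C1D1 to the first target-dose day: C1D8 for 1-step, C1D15 for 2-step.
- Add a hematology mark on Day 16 for 2-step patients, drawn with the 24-hour PK and cytokine samples already due then.

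In SAP Section 8.5, cite Table 13-13 beside Table 7-2, which is the only ECG schedule it now names.

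The ECG count is unchanged, and each 2-step patient gives one extra blood tube during an existing draw. The downside is that the lead-in dose loses its scheduled post-infusion ECG. That level, 30 mcg in SAP Table 1, has already been given to 5 fixed-dose patients. A sponsor who wants to keep that reading can add the target-day ECG instead of moving it, at the cost of one more ECG per patient. The 9 IPE patients already enrolled in SAP Table 1 may be past the point where the change helps.

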13.5 Detailed Description and Rationale for Changes

13.5.1 Amendment 3

Section	Change	Rationale
Multiple	The generic name “tebentafusp” is used throughout for IMCgp100	To use current nomenclature
Synopsis	The synopsis was updated as needed to reflect the changes below	To ensure consistency
Section 1.4	Added clinical experience in ongoing study as of 22Jan2020	To provide current enrollment and safety information for the study
Section 5.3	The exclusion criterion for minimum creatinine clearance was decreased from 50 mL/min to 40 mL/min	Especially in urothelial carcinoma, patients with advanced cancers may have decreased renal function but are not anticipated to be at elevated risk for treatment-related toxicities
Section 5.3	The exclusion criterion for congestive heart failure was updated to add the word “diagnosed”: Clinically significant and/or uncontrolled heart disease such as diagnosed congestive heart failure (New York Heart Association Class ≥ 2)	To clarify that the exclusion is for diagnosed congestive heart failure rather than signs and symptoms that could be confused with Class 2 congestive heart failure (mild symptoms [mild shortness of breath and/or angina] and slight limitation during ordinary activity) but are due to other causes
Section 5.3	The exclusion criterion for ongoing \geq Grade 2 toxicity due to prior cancer therapy was updated so that any Grade 2 endocrine disorder [on stable replacement doses and without symptoms] is an exception; previously this exception was limited to hypothyroidism	Other Grade 2 endocrine disorders may occur due to prior cancer therapy and are not anticipated to be associated with an elevated risk for treatment-related toxicities if asymptomatic and clinical stable on replacement therapy

Section	Change	Rationale
Section 5.3	In the exclusion criterion for antibiotic use, the washout period for oral antibiotics was reduced from 14 days to 7 days prior to the first dose of study drug (note: there was no change to the washout period for IV antibiotics).	Patients who responded to oral antibiotics, completed treatment at least 7 days before the first dose of study drug, and meet all other eligibility criteria are not anticipated to be at an elevated risk for treatment-related toxicities
Section 6.2	Added that after Phase I is completed and the SST has reviewed all available relevant data for at least 6 patients at the RP2D, the SST may decide to reduce the minimum required monitoring time to no less than 8 hours post-end of infusion on C1D1, C1D8, and/or C1D15 (with longer hospitalization if indicated) during the Phase II portion of the study.	Based on the observation that all signs/symptoms of CRS, to date, have occurred rapidly (within a few hours) following administration of IMCnyeso, and provided the initial assessment of safety at the RP2D supports the dose as being well-tolerated and any signs/symptoms suggestive of CRS occur within 2-4 hours post-end of infusion, then monitoring for 8 hours post-end of infusion provides an adequate safety margin
Section 6.4	If the Cycle 1 Day 1 dose is \leq 30 mcg, the infusion may be given over 1 hour rather than 2 hours	Based on emerging safety data, an initial dose of \leq 30 mcg infused over 1hour is anticipated to be tolerable and would simplify study conduct
Section 6.10.1	For any allowed dose escalation step, an option was added to switch from a fixed-dose regimen to a 1-step or 2-step IPE regimen (or from a 1-step to a 2-step IPE regimen as applicable). Figure 6-3, which shows representative escalation paths with IPE options, was updated accordingly.	Initial assessment of a new higher dose level is anticipated to present less risk when IPE regimen is used instead of a fixed-dose regimen
Section 6.10.1 and 6.10.2	The DLT observation period is 28 days for all regimens (previously the DLT observation period was extended for intrapatient escalation regimens)	The DLT observation period is designed to allow detection of acute treatment-related toxicities, which are anticipated to occur within the first 28 days of treatment, regardless of regimen

Section	Change	Rationale
Section 6.10.1	Added an option for patients who were enrolled in a lower dose cohort to move to a higher dose level after the higher dose level has successfully completed SST review, if the patient has completed at least 3 cycles of treatment, and has tolerated treatment well	To allow patients to receive a dose level that may provide more therapeutic benefit, with appropriate safeguards for safety
Section 6.13	Added that non-live vaccines are not to be administered within 14 days before and 28 days after the first dose of IMCnyeso treatment, and thereafter not within 24 hours before or after IMCnyeso treatment, and live or attenuated vaccines are prohibited from 28 days prior to the first dose of IMCnyeso until 30 days after the last dose of IMCnyeso	Vaccine-related adverse events may be exacerbated by immune activation associated with IMCnyeso treatment
Section 7	Schedule of Assessments Tables 7-1 and 7-2 were updated to reflect changes in Section 7.4.4 shown below	To ensure consistency between the Schedule of Assessments tables and the body of the protocol
Section 7	In the Schedule of Treatment Period Assessments table (Table 7-2), inconsistencies between the main table and footnote were resolved	Correction of typographical errors
Section 7	The sample collection for pharmacokinetics at the Cycle 1 Day 2 36-hour post-EOI timepoint is optional rather than mandatory	To aid in protocol compliance
Section 7.4.4	Follicle-stimulating hormone is to be done only if required to confirm non-childbearing potential, rather than required for all post-menopausal women	It is not necessary to test FSH in all post-menopausal women
Section 7.4.4	Added that blood oxygen saturation should be assessed at Screening and for at least the first 3 treatment cycles	Monitoring oxygen saturation may aid in detection and management of cytokine release syndrome

Section	Change	Rationale
Section 13.1.1	Added that if dose escalation proceeds to a dose of >150 mcg according to the BLRM and treatment at this dose level is well-tolerated, additional BLRM simulations may be performed to predict rates of toxicity for higher dose levels	To enable consideration of higher doses if supported by emerging safety data
Section 13.4	The sample collection for pharmacokinetic and central lab cytokine assessments at 12 hours post end of infusion are optional rather than mandatory	To aid in protocol compliance

13.5.2 Amendment 2

Section in Amendment 1	Change	Rationale
Cover page	Updated sponsor contact information	The study has a new Medical Monitor
Synopsis	The synopsis was updated as needed to reflect the changes below	To ensure consistency
Synopsis	Inclusion / exclusion criteria, study objectives, and rationale for selection of the starting dose were removed from the synopsis	To simplify the synopsis and prevent potential inconsistencies
Synopsis	Updated to “Based on the available IMCnyeso preclinical data and clinical safety information from the related ImmTAC molecule IMCgp100, IMCnyeso may induce rash, tumor flare/pain, lymphopenia (associated with lymphocyte trafficking), and cytokine release syndrome. Conservative monitoring and management guidelines as well as definitions of DLT have been implemented”	To provide more current and comprehensive summary of risk information rather than focusing primarily on potential for skin toxicity
Section 1.1	IMCnyeso is a “bispecific protein therapeutic” rather than “bispecific biologics”	To clarify that IMCnyeso is a protein

Section in Amendment 1	Change	Rationale
Section 1.2	Simplified language describing mechanism of action	To clarify the mechanism of action of IMCnyeso
Section 1.2	Updated mechanism of action statement to add sentence: "In addition, IMCnyeso-mediated tumor lysis may prime an endogenous anti-tumor immune response"	To add a description of a second potential mechanism of action based on emerging data from other ImmTAC clinical trials
Section 1.2	Information about NY-ESO-1 / LAGE-1A testing removed from this section and consolidated in Section 1.5 (screening strategy) and Section 7.4.1 (description of assessments)	Removed redundant information
Section 1.3	Consolidated description of species specificity of IMCnyeso at the start of Section 1.3 and removed this information from the following sub-sections	Removed redundant information
Section 1.4	Added clinical experience in ongoing study as of 26Apr2019	To provide current enrollment and safety information for the study
Section 1.4	Cytokine release syndrome (CRS) section updated to add: Release of pro-inflammatory cytokines (eg, IL-6, IFN- γ , TNF- α) is a predicted pharmacodynamic effect of IMCnyeso. Based on experience with IMCgp100, symptoms such as pyrexia, chills, nausea, hypotension, and edema were observed in most patients, typically 4-24 hours after the first 2-3 doses. As of August 2018, 2% of patients in the IMCgp100-102 study experienced severe (Grade 3) CRS with IMCgp100	To provide more current and comprehensive risk information
Section 1.4	Added that IMCnyeso may cause inflammation within the tumor microenvironment. Depending on the location of the tumors, various AEs may occur, including hepatic events and pulmonary events	To provide more current and comprehensive risk information

Section in Amendment 1	Change	Rationale
Section 1.5	Added that target expression frequencies are significantly lower in uveal melanoma and NSCLC adenocarcinoma	To provide additional information regarding target antigen expression
Section 1.6.4	A reference was added regarding treatment options for patients with synovial sarcoma	To provide a more current reference
Section 2.1, Section 6.4	The Study Safety Team will include Study Investigators, Sponsor Medical Monitor, and a statistician (role of independent medical oncologist removed)	For operational simplicity and to align with standard practice for FIH studies
Section 2.2	Description of measures taken to minimize risks for patients in the study updated to include “eligibility criteria designed to exclude patients at potentially high risk for experiencing treatment-related toxicity”	To correct an omission
Section 3, Section 9	A substantial amount of redundant information was removed; hyperlinks were added to the relevant sections where information is located	To remove redundant information
Section 3, Section 9.9.1	The estimated number of patients in Phase I is 27. In 80% of simulations conducted, the sample size was < 33 patients	Estimated patient numbers were updated to reflect results of the new BLRM simulations
Section 3, Section 9.9.2	Simon 2-stage design incorporated for Phase II with initial enrollment of 9 patients and option to enroll 15 additional patients if there is at least one response. A formal interim analysis was added to Phase II	To enable more robust assessment of efficacy and provide justification for the Phase II sample size
Section 3.4	Redundant information regarding study periods was deleted from Section 3.4 and assessment details moved to Section 7	To remove redundant information and improve organization
Section 3.4, Section 7.3, and others	Safety follow-up changed to 30 days (from 90 days)	30-day safety follow-up is appropriate based on the <24-hour half-life of ImmTAC

Section in Amendment 1	Change	Rationale
Section 3.5	Substantially shortened. Criteria for treatment discontinuation consolidated in Section 6.16	To remove redundant information and improve organization
Section 3.6	Clarified requirements for planned End of Study, including requiring that secondary endpoints of objective response, overall survival, progression-free survival, and duration of response have been adequately assessed in all subjects	To ensure that study objectives and endpoints are adequately assessed before End of Study
Section 4	Redundant body text was removed; objectives and corresponding endpoints are shown in table format only	Removed redundant information and improve organization
Section 2.1, Section 3.1, Section 4	The primary objective for Phase II was changed from “to further explore the safety and tolerability of the identified RP2D” to preliminary efficacy (BOR per RECIST v.1.1). Safety and tolerability is a secondary objective for Phase II.	To align with the goals of the Phase II portion of the study
Section 4	A secondary efficacy objective (based on RECIST v1.1) was added for Phase I	Efficacy is evaluated in Phase I but previously was not associated with a study objective
Section 4, Section 7	Response will no longer be evaluated per modified irRECIST	To simplify study conduct and align with current standards in the field
Section 4	The secondary PK endpoint was clarified to indicate that serum PK parameters would be determined after single and multiple doses	To clarify scope of planned analysis
Section 4	The secondary ADA endpoint was updated to include the impact of ADA on PK	To clarify scope of planned analysis
Section 4	[REDACTED]	[REDACTED]

Section in Amendment 1	Change	Rationale
Section 4	[REDACTED]	[REDACTED]
Section 4	[REDACTED]	[REDACTED]
Section 5.1	Shortened description of patient population	To remove redundant information
Section 5.2, Section 5.3	Organized eligibility criteria by topic and simplified	To aid in protocol compliance
Section 5.2	Clarified prior treatment requirements for Phase I to “Patients must be relapsed from, refractory to, or intolerant to all approved and available classes of therapy known to provide clinical benefit for their condition”	To clarify study inclusion criteria
Section 5.2	Clarified prior treatment requirements for Phase II to note that required therapies may have been given in the adjuvant setting if disease progression occurred during or within 6 months of completing adjuvant therapy, and patients with NSCLC with a genomic tumor aberration (eg, EGFR, ALK) that is targeted by Health Authority-approved agent(s) must be relapsed from, refractory to, or intolerant of relevant targeted agent(s).	To align with standard of care
Section 5.3	Allow patients with Grade 2 hypophosphatemia [if receiving appropriate replacement therapy] or hypothyroidism [if on stable replacement doses] due to prior cancer therapy to enroll	Hypophosphatemia due to prior ifosfamide and hypothyroidism due to prior checkpoint inhibitors are relatively common in the eligible patient population and are not expected to be exacerbated by IMCnyeso treatment

Section in Amendment 1	Change	Rationale
Section 5.3	Patients with leptomeningeal disease or cord compression are not eligible for study participation	To ensure adequate baseline health status of enrolled patients
Section 5.3	Clarify that hematology evaluations used to determine study eligibility must be performed \geq 7 days from any blood or blood product transfusion and \geq 14 days from any dose of hematologic growth factor; removed exclusion criteria regarding use of hematopoietic growth factors and erythroid stimulating agents	To ensure that enrolled patients have adequate hematologic function and simplify the protocol
Section 5.3	Eligibility criteria for renal function will be based only on creatinine clearance, rather than creatinine concentration and/or creatinine clearance	To reduce ambiguity in eligibility criteria
Section 5.3	Added for patients with Gilbert's syndrome exclude if total bilirubin $> 3.0 \times$ ULN or direct bilirubin $> 1.5 \times$ ULN	Slightly elevated bilirubin in patients with Gilbert's syndrome is not a safety concern for IMCnyeso
Section 5.3	Reduced minimum absolute lymphocyte count needed for eligibility to $<0.5 \times 10^9/L$ (previously $1.0 \times 10^9/L$)	Grade 2 lymphopenia is a relatively common finding in patients with advanced cancers and is not expected to impact the safety or efficacy of IMCnyeso
Section 5.3	Removed electrolyte lab abnormalities from exclusion criteria	Electrolyte abnormalities can be appropriately managed and should not be exclusionary
Section 5.3	Removed exclusion criterion for prior hypersensitivity to other biologic drugs or monoclonal antibodies	Prior hypersensitivity to another biologic drug does not necessarily indicate elevated risk of hypersensitivity to IMCnyeso
Section 5.3	Systemic antibiotics must be completed at least 14 days prior to the first dose of study drug (rather than prior to screening)	To improve operational feasibility while maintaining appropriate safeguards

Section in Amendment 1	Change	Rationale
